9 PHARMACOVIGILANCE

9.1 Definitions

Term	Definition
Adverse Event (AE)	
Any untoward medical occurrence in a participant to whom a medicinal product has been administered, including occurrences which are not necessarily caused by or related to that product.
 
Clinical outcomes (e.g. moderate exacerbations not requiring hospitalisation) are exempt from adverse event recording and will be captured on the relevant case report form.

Adverse Reaction (AR)	
Any untoward and unintended response in a participant to an investigational medicinal product which is related to any dose administered to that participant.
 
The phrase "response to an investigational medicinal product" means that a causal relationship between a trial medication and an AE is at least a reasonable possibility, i.e. the relationship cannot be ruled out.
 
All cases judged by either the reporting medically qualified professional or the Sponsor as having a reasonable suspected causal relationship to the trial medication qualify as adverse reactions. It is important to note that this is entirely separate to the known side effects listed in the SmPC. It is specifically a temporal relationship between taking the drug, the half-life, and the time of the event or any valid alternative aetiology that would explain the event.

Serious Adverse Event (SAE)	
A serious adverse event is any untoward medical occurrence that:
 
 • results in death • is life-threatening • results in persistent or significant disability/incapacity • consists of a congenital anomaly or birth defect 
Other 'important medical events' may also be considered serious if they jeopardise the participant or require an intervention to prevent one of the above consequences.
 
NOTE: The term "life-threatening" in the definition of "serious" refers to an event in which the participant was at risk of death at the time of the event; it does not refer to an event which hypothetically might have caused death if it were more severe.
 
Clinical outcomes that require inpatient hospitalisation or prolongation of existing hospitalisation are exempt from serious adverse event reporting, unless the investigator deems the event to be related to the administration of the study drug. Clinical details about these outcomes will be routinely collected in the case report form.

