Serious Adverse Reaction (SAR)	
An adverse reaction deemed to be serious (i.e. results in death, is life-threatening, results in persistent or significant disability/incapacity, consists of a congenital anomaly or birth defect.) and, in the opinion of the reporting Investigator, believed with reasonable probability to be due to one of the trial treatments, based on the information provided.

Suspected Unexpected Serious Adverse	
A serious adverse reaction, the nature and severity of which is not consistent with the information about the medicinal product in question set out in the reference safety information:

Reaction (SUSAR)	
 • in the case of a product with a marketing authorisation, this could be in the summary of product characteristics (SmPC) for that product, so long as it is being used within its licence. If it is being used off label an assessment of the SmPCs suitability will need to be undertaken. • in the case of any other investigational medicinal product, in the investigator's brochure (IB) relating to the trial in question
-------------------------	---

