9.2 Recording and reporting of SAEs, SARs AND SUSARs

All SAEs / SUSARs occurring following first administration of IMP/placebo until the final trial visit (week 48/Final Follow-up) or 28 days post cessation of trial treatment where this occurs earlier than protocolised (the length of the withdrawal period of mepolizumab; please see pharmacokinetic details within section 5.2 of the Summary of Product Characteristics), must be recorded on the SAE Form and sent to the Sponsor and the Leicester Clinical Trials Unit (LCTU) within 24 hours of the research staff becoming aware of the event. The LCTU will work with Sponsor to review and track all SAEs. Once all resulting queries have been resolved, the Sponsor will send an acknowledgement of the closure of the SAE, all correspondence and signed SAE forms will be retained in the Investigator Site File, within the Trial Master File and electronically on the Sponsor SAE database.

For each SAEs / SUSARs the following information will be collected:

- full details in medical terms and case description
- event duration (start and end dates when deemed serious, if applicable)
- action taken
- outcome
- seriousness criteria
- Causality (i.e. relatedness to trial drug / investigation), in the opinion of the investigator whether the event would be considered anticipated.

Any change of condition or other follow-up information should be sent to the Sponsor as soon as it is available or at least within 24 hours of the information becoming available. Events will be followed up until the event has resolved or a final outcome has been reached.

All SAEs assigned by the CI or delegate (or following central review) as both suspected to be related to IMP-treatment and unexpected will be classified as SUSARs and will be subject to expedited reporting to the Medicines and Healthcare Products Regulatory Agency (MHRA). The sponsor will inform the MHRA and the REC of SUSARs within the required expedited reporting timescales. Fatal or life-threatening SUSARs must be reported within 7 days and all other SUSARs within 15 days.

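### The SAR definition in protocol 9.1 conflicts with the AR and SAE definitions and with the SUSAR rule in 9.2, so a drug-suspected admission is classified differently depending on which text is followed

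*Protocol*

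**What the plan says.** The definitions are in the table of protocol Section 9.1.

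- **Adverse reaction (AR).** The test is that "a causal relationship between a trial medication and an AE is at least a reasonable possibility, i.e. the relationship cannot be ruled out". Two parties may make the judgement: "All cases judged by either the reporting medically qualified professional or the Sponsor as having a reasonable suspected causal relationship" to the trial medication count as adverse reactions.
- **Serious adverse event (SAE).** There are four listed criteria, followed by a sentence that other important medical events may also be considered serious. Hospitalisation is not among the four. It appears only in a note that exempts hospitalised clinical outcomes from SAE reporting, "unless the investigator deems the event to be related to the administration of the study drug".
- **Serious adverse reaction (SAR).** This is an adverse reaction that is serious, with seriousness spelled out after an i.e. as: "results in death, is life-threatening, results in persistent or significant disability/incapacity, consists of a congenital anomaly or birth defect". It must also be, in the reporting investigator's opinion, "believed with reasonable probability to be due to one of the trial treatments".
- **SUSAR.** This is a serious adverse reaction that does not fit the reference safety information.

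Section 9.2 then gives a working rule. SAEs that the Chief Investigator (CI) or a delegate, or a central review, finds "both suspected to be related to IMP-treatment and unexpected will be classified as SUSARs". The reporting limits are 7 days for fatal or life-threatening SUSARs and 15 days for the rest.

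**The concern.** Causality and seriousness are separate properties. A SAR should be an AR that is also serious, so adding seriousness should change neither the causality threshold nor who may judge it, and the seriousness criteria should be those of the SAE entry. Section 9.1 departs from this on all three counts, and its SUSAR definition inherits the departures.

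The point matters more here than in most trials. All-cause readmission is part of the primary outcome, and the sample size section assumes that 65% of usual-care patients have a readmission or death by 48 weeks. Admissions will be common, and hospitalised clinical outcomes are exempt from SAE reporting by default. The relatedness judgement is therefore the main filter that returns a drug-caused admission to safety reporting, and the protocol states that judgement in conflicting ways. Two trained staff could classify the same event differently while a regulatory time limit is running.

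**Working it through.** No figure is at issue, so the check is a side-by-side reading followed by a trace of test cases.

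| | AR (9.1) | SAE (9.1) | SAR (9.1) | SUSAR rule (9.2) |
|---|---|---|---|---|
| Causality | Reasonable possibility, not excluded | None, except to lift the hospitalisation exemption | Reasonable probability | Suspected |
| Judge | Reporting professional or Sponsor | Investigator, for the exemption | Reporting investigator | CI or delegate, or central review |
| Seriousness | Not applicable | Four criteria, plus important medical events; drug-related hospitalised outcomes by implication | The four criteria only | Any SAE |

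**Case 1. Drug-suspected, unexpected, leads to admission; not fatal, life-threatening or disabling, and no congenital anomaly.** Under 9.1 it meets none of the four SAR criteria, so it is not a SAR and hence not a SUSAR. Under the SAE entry, a hospitalised clinical outcome that the investigator deems related loses its exemption and is reportable; other such events may enter as important medical events. Under 9.2, that SAE is a SUSAR with the 15-day limit. The two sections give opposite answers.

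**Case 2. The same event, but expected.** It is not a SUSAR under either section, which is as intended. It is also not a SAR under 9.1, and no other text makes it one. Section 9.3 assigns tasks by the SAR label: CI review of specific SAEs and SARs, MedDRA coding, and Sponsor collection and verification. The event is handled there as an SAE only.

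**Case 3. Life-threatening, with a drug relation that is possible but not probable.** The SAR seriousness list is met. The AR test is met. Whether the SAR causality wording is met is unclear. Under 9.2 the event is a SUSAR if it is suspected and unexpected. Section 7.5 also works from a threshold of at least possibly related when it refers to serious events, so the AR entry, 7.5 and 9.2 agree and the SAR entry differs.

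**Case 4. The Sponsor, but not the reporting investigator, suspects the drug.** The event is an AR, but not a SAR on the wording. If it is a hospitalised clinical outcome, the exemption is lifted only by the investigator's judgement, so on a literal reading it may not become an SAE and so may not reach the 9.2 rule.

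**Control case. An admission that is also fatal, life-threatening or disabling and is judged probably related by the investigator.** It meets the SAR definition, and 9.1 and 9.2 agree.

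**The case against.** A reader might infer that a drug-suspected admission can never become a SUSAR and would miss the 7- or 15-day limits. The documents do not support that. The rule in 9.2 starts from SAEs, not SARs, needs only suspicion, and is open to the CI, a delegate or central review. Case 1 therefore has a route to expedited reporting, in the same section that sets the limits.

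A reader might also cite the hypersensitivity reactions named in Section 8.11, such as bronchospasm or angioedema, as SUSARs that would be lost. That section describes them as already observed with mepolizumab. They may be expected under the reference safety information, which is not among the documents, and would then not be SUSARs under any wording.

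Three further points are fair:

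- The SAR entry begins by calling the event an adverse reaction, which imports the lower threshold, so the later phrase may be loose drafting. For the same reason, and because the SAP's adverse event template gives no cut-point across its five relatedness grades, one cannot say that the grade possible definitely fails the SAR wording.
- Section 7 of the SAP and its templates tabulate events by seriousness and by relatedness separately. No SAR count is planned.
- Section 9.3 names SAEs beside SARs in these tasks, so an event that misses the SAR label is not outside review.

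These points limit the consequence but do not remove the contradiction. Section 9.2 helps only when the event has been reported as an SAE and is unexpected. Hospitalisation reaches SAE status only by implication, through an exception that depends on one person's judgement. Nothing covers the expected events of case 2.

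**Conclusion.** The SAR definition is wrong as written. It raises causality from possibility to probability, restricts the judgement to the reporting investigator, and drops both important medical events and drug-related hospitalisation. Sections 9.1 and 9.2 then disagree on whether an unexpected, drug-suspected admission short of the four criteria is a SUSAR, and for an expected one no text restores SAR status.

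The size cannot be stated in events, because the documents give no rate of drug-suspected admissions. The effect is inconsistent classification, not a closed route to expedited reporting. The primary analysis and the planned safety tables do not use the SAR label. This is a correction well worth making for the safety reporting, but it does not put the trial's main conclusion at risk.

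The conclusion rests on two readings: that the i.e. closes the SAR seriousness list, and that probability is meant as a stronger word than possibility. If the second is only loose drafting, the mismatches in who may decide and in seriousness remain.

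**What to change.** Reconcile the entries in 9.1 with each other and with 9.2:

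1. Define a SAR as an adverse reaction, with the AR entry's threshold of reasonable possibility and its two judges (reporting professional or Sponsor), that meets any criterion of the SAE entry, including important medical events.
2. State in the SAE entry that hospitalisation or its prolongation deemed drug-related counts as serious. Keep the existing exemption for clinical outcomes not deemed related. Listing hospitalisation as a general criterion without that limit could bring unattributed admissions into the SAE rate, which is a listed outcome.
3. Make the 9.1 SUSAR definition match the 9.2 rule.

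The cost is a change of wording and possibly a few more SAR or expedited reports.

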9.2 Recording and reporting of SAEs, SARs AND SUSARs

All SAEs / SUSARs occurring following first administration of IMP/placebo until the final trial visit (week 48/Final Follow-up) or 28 days post cessation of trial treatment where this occurs earlier than protocolised (the length of the withdrawal period of mepolizumab; please see pharmacokinetic details within section 5.2 of the Summary of Product Characteristics), must be recorded on the SAE Form and sent to the Sponsor and the Leicester Clinical Trials Unit (LCTU) within 24 hours of the research staff becoming aware of the event. The LCTU will work with Sponsor to review and track all SAEs. Once all resulting queries have been resolved, the Sponsor will send an acknowledgement of the closure of the SAE, all correspondence and signed SAE forms will be retained in the Investigator Site File, within the Trial Master File and electronically on the Sponsor SAE database.

For each SAEs / SUSARs the following information will be collected:

- full details in medical terms and case description
- event duration (start and end dates when deemed serious, if applicable)
- action taken
- outcome
- seriousness criteria
- Causality (i.e. relatedness to trial drug / investigation), in the opinion of the investigator whether the event would be considered anticipated.

Any change of condition or other follow-up information should be sent to the Sponsor as soon as it is available or at least within 24 hours of the information becoming available. Events will be followed up until the event has resolved or a final outcome has been reached.

All SAEs assigned by the CI or delegate (or following central review) as both suspected to be related to IMP-treatment and unexpected will be classified as SUSARs and will be subject to expedited reporting to the Medicines and Healthcare Products Regulatory Agency (MHRA). The sponsor will inform the MHRA and the REC of SUSARs within the required expedited reporting timescales. Fatal or life-threatening SUSARs must be reported within 7 days and all other SUSARs within 15 days.

9.3 Responsibilities

Principal Investigator (PI) or suitably trained delegate:

1. Checking for AEs when participants attend for treatment / follow-up.
2. Using medical judgement in assigning seriousness, causality and whether the event was anticipated using the Reference Safety Information approved for the trial.
3. Ensuring that all SAEs are recorded and reported to the sponsor within 24 hours of becoming aware of the event and provide further follow-up information as soon as available. Ensuring that SAEs are chased with Sponsor if a record of receipt is not received within 2 working days of initial reporting.

4. Ensuring that AEs and ARs are recorded and reported to the sponsor in line with the requirements of the protocol.

Chief Investigator (CI) / delegate or independent clinical reviewer:

1. Clinical oversight of the safety of patients participating in the trial, including an ongoing review of the risk / benefit.
2. Using medical judgement in assigning AEs seriousness, causality and whether the event was anticipated (in line with the Reference Safety Information) where it has not been possible to obtain local medical assessment.
3. Immediate review of all SUSARs.
4. Review of specific SAEs and SARs in accordance with the trial risk assessment and protocol as detailed in the Trial Monitoring Plan.
5. Assigning Medical Dictionary for Regulatory Activities (MedDRA) or Body System coding to all AEs, SAEs and SARs.
6. Preparing the clinical sections and final sign off of the Development Safety Update Report (DSUR).

Sponsor: (NB where relevant these can be delegated to CI)

1. Central data collection and verification of AEs, ARs, SAEs, SARs and SUSARs according to the trial protocol onto a database.
2. Reporting safety information to the CI, delegate or independent clinical reviewer for the ongoing assessment of the risk / benefit according to the Trial Monitoring Plan.
3. Reporting safety information to the independent oversight committees identified for the trial (Data Safety Monitoring Committee (DSMC) and / or Trial Steering Committee (TSC) according to the Trial Monitoring Plan.
4. Expedited reporting of SUSARs to the Competent Authority (MHRA in UK) and REC within required timelines.
5. Notifying Investigators of SUSARs that occur within the trial.
6. The unblinding of a participant for the purpose of expedited SUSAR.
7. Checking for (annually) and notifying PIs of updates to the Reference Safety Information for the trial.
8. Preparing standard tables and other relevant information for the DSUR in collaboration with the CI and ensuring timely submission to the MHRA and REC.

Trial Steering Committee (TSC):

In accordance with the Trial Terms of Reference for the TSC, periodically reviewing any safety issues highlighted by the DSMC and acting upon them appropriately.

Data Safety Monitoring Committee (DSMC):

In accordance with the Trial Terms of Reference for the DSMC, periodically reviewing overall safety data to determine patterns and trends of events, or to identify safety issues, which would not be apparent on an individual case basis.

9.5 Pregnancy and pregnancy reporting

Limited data is available on the use of mepolizumab during pregnancy. Mepolizumab crosses the placental barrier in monkeys. Animal studies do not indicate reproductive toxicity. The potential for harm to a human foetus is unknown. The manufacturer advises to avoid use during pregnancy unless the benefit outweighs risk.

MHRA guidelines (http://www.hma.eu/fileadmin/dateien/Human_Medicines/01-About_HMA/Working_Groups/CTFG/2014_09_HMA_CTFG_Contraception.pdf accessed from <https://www.gov.uk/government/publications/common-issues-identified-during-clinical-trial-applications/common-issues-clinical>) for use of IMPs with an unlikely risk of human teratogenicity / fetotoxicity advise that women of child-bearing potential (WOCBP) must have a negative blood serum pregnancy test performed prior to first administration of trial treatment, a negative urine pregnancy test at each subsequent visit prior to dosing, and must agree to use an acceptable method of birth control for the duration of the trial. However, given the average age range of the disease population, this will not be a significant proportion of participants. Additional testing will also occur at any time during the trial if a menstrual period is missed or as required by local law.

A woman is defined as being of childbearing potential (WOCBP), i.e. fertile, following menarche and until becoming post-menopausal, unless permanently sterile. Permanent sterilisation methods include hysterectomy, bilateral salpingectomy and bilateral oophorectomy. A postmenopausal state is defined as no menses for 12 months without an alternative medical cause.

Acceptable birth control methods that result in a failure rate of more than 1% per year include:

- progestogen-only oral hormonal contraception, where inhibition of ovulation is not the primary mode of action
- male or female condom with or without spermicide
- cap, diaphragm or sponge with spermicide

Additional, highly effective contraceptive measures (i.e. a failure rate of less than 1% per year when used consistently and correctly) may also be used. These are defined as:

- combined (estrogen and progestogen containing) hormonal contraception associated with inhibition of ovulation:
 - oral
 - intravaginal
 - transdermal
- progestogen-only hormonal contraception associated with inhibition of ovulation:
 - oral
 - injectable
 - implantable
- intrauterine device (IUD)
- intrauterine hormone-releasing system (IUS)
- bilateral tubal occlusion

- vasectomised partner (provided that partner is the sole sexual partner of the WOCBP trial participant and that the vasectomised partner has received medical assessment of the surgical success)
- sexual abstinence (defined as refraining from heterosexual intercourse during the entire period of risk associated with the study treatments).

All pregnancies within the trial (either the trial participant or the participant's partner, with consent) should be reported to the Chief Investigator, the LCTU and the Sponsor using the relevant Pregnancy Reporting Form within 24 hours of notification.

Pregnancy is not considered an AE unless a negative or consequential outcome is recorded for the mother or child/foetus. If the outcome meets the serious criteria, this would be considered an SAE.

The pregnancy must be followed up to determine outcome (including premature termination) and status of mother and child in accordance with Sponsor and local reporting requirements and timelines.

Any SAE occurring in association with a pregnancy, brought to the investigator's attention after the participant has completed the trial, and considered by the investigator as possibly related to the trial treatment, must be promptly reported to sponsor in accordance with Sponsor and local reporting requirements and timelines.

9.6 Overdose

The dose of mepolizumab considered to be an overdose has not been defined. Single doses of up to 1500 mg were administered intravenously in a clinical trial to patients with eosinophilic disease without evidence of dose-related toxicities. There are no known antidotes. The investigator should use clinical judgement in treating the symptoms of a suspected overdose.

9.7 Reporting urgent safety measures

If any urgent safety measures are taken the CI/Sponsor shall immediately and in any event no later than 3 days from the date the measures are taken, give written notice to the MHRA and the relevant REC of the measures taken and the circumstances giving rise to those measures.

Please refer to the following website for details on clinical trials safety reporting:
<http://www.mhra.gov.uk/Howweregulate/Medicines/Licensingofmedicines/Clinicaltrials/Safetyreporting-SUSARsandASRs/index.htm>

9.8 The type and duration of the follow-up of participants after adverse reactions.

Following an adverse reaction (AR) the participants will be followed-up for an appropriate length of time as dictated by the nature of AR and their clinical needs. ARs will continue to be recorded and reported for up to 4 weeks after the last dose of IMP has been administered. Any SUSAR will need to be reported to the Sponsor irrespective of how long after IMP administration the reaction has occurred until resolved.

